## CHAPTER 1 BACKGROUND & STUDY SYNOPSIS

132  
133  
134  
135  
136

This study is being conducted by the Pediatric Eye Disease Investigator Group (PEDIG). It is one of a series of randomized trials and observational studies that address management issues related to the treatment of amblyopia in children.

### 1.1 Study Objective

137  
138  
139  
140  
141

To compare the effectiveness of patching combined with active vision therapy plus near activities versus patching combined with control vision therapy plus near activities for moderate amblyopia (20/40-20/100) in 7 to <13 year olds.

### 1.2 Rationale for the Study

142  
143  
144  
145  
146  
147  
148  
149  
150  
151  
152  
153  
154  
155  
156  
157  
158  
159  
160  
161

Patching and atropine have been traditionally used for the improvement of visual acuity in children with amblyopia. Previous studies have shown that these methods of treatment are effective in young children with functional amblyopia. More recently ATS3[1], a randomized clinical trial of 507 children ages 7-<18, found that part-time patching combined with atropine and near activities improved visual acuity by two or more lines in 53% of the 7 to 12 year olds compared to 25% for optical correction alone. For the 13 to 17 year olds, part-time patching and near activities improved visual acuity by 2 or more lines in 25%, compared to 23% for optical correction alone. While it appears that patching and/or atropine, combined with near activities, can improve visual acuity in some patients ages 7-<18, most patients in the study were left with residual visual acuity deficits. To further improve visual acuity and binocularity in children with amblyopia some eye care providers augment these traditional therapies with vision therapy. Vision therapy is prescribed initially if there is moderate amblyopia with stereopsis. Vision therapy can be added to the treatment regimen once the patient has reached moderate levels of vision loss with stereopsis or if the patient is not responding to the current treatment and still has moderate amblyopia. It is thought that the best candidates for this type of therapy are those children with a minimum level of stereopsis (at least 800") and without constant strabismus. Those children with no stereopsis would not be able to perform the activities in the later stages of therapy utilizing binocular vision.

162  
163  
164  
165  
166  
167

Vision therapy is a sequence of prescribed activities typically performed on a daily basis at home and weekly in-office, and is directed toward an individual patient's deficient skills. Visual skills are practiced under conditions that provide the patient with feedback. The feedback, along with a gradual increase in the demand of the activities as improvement occurs, enables the patient to improve visual functions such as visual acuity, fixation, accommodation, and vergence skills.

168  
169  
170  
171  
172  
173  
174  
175  
176  
177  
178  
179

There have been case reports and small sample studies that have shown that vision therapy in combination with spectacles and occlusion is effective in improving the visual acuity of patients with amblyopia.[2-6] Wick et al[4] looked at nineteen patients who were diagnosed with anisometric amblyopia between the ages of 6 to 49. Seventeen of the patients had moderate amblyopia and two had severe amblyopia, based on the definition of amblyopia used in the Amblyopia Treatment Studies. The patients were treated with a sequence that included spectacle correction, occlusion therapy and both monocular and binocular vision therapy. The outcomes were presented as final visual acuity in the amblyopic eye and the Amblyopia Success Index (ASI), used by Meyer et al.[7] The ASI compares the actual visual acuity result with the maximum improvement of vision. The results are reported as a percent between 0% and 100%. Patients having a result of 0% indicate that they did not have any improvement in final visual

180 acuity compared to initial acuity. Patients with a result of 100% indicate that their visual acuity  
181 reached the maximum level of improvement (20/20) over the course of therapy. Thirteen of the  
182 seventeen patients with moderate amblyopia had a final visual acuity of 20/25 or better and all of  
183 the patients with moderate amblyopia had 20/30 or better final visual acuity. The mean ASI for  
184 the moderate group was 92.67%.

185  
186 Wick et al. also compared his patients older than ten with the Meyer cohort to see if there was  
187 any difference in the ASI between the two groups. Meyer's patients improved an average of  
188 43.7% with constant occlusion and spectacle wear, while Wick's patients improved an average  
189 of 92.6% with occlusion (2-5 hours per day), spectacle wear and sequential vision therapy. Wick  
190 et al. makes the assessment that the amount of patching is not the determining factor for  
191 improvement in visual acuity. They further state that in older patients in order to reach  
192 maximum visual acuity spectacle, occlusion and vision therapy are required.[4]

193  
194 More recent reports on "perceptual learning," an active form of therapy in which amblyopic  
195 subjects practice a position-discrimination task, have shown a mean acuity improvement of  
196 approximately 30% (two lines) in amblyopic children and adults who had completed occlusion  
197 therapy.[8-10] These studies provide support for the notion that the practice of particular visual  
198 skills under conditions that provide the patient with feedback (e.g., vision therapy) may be  
199 beneficial in improving the visual performance of amblyopic eyes.

200  
201 The second reason to prescribe active therapy is to enhance or facilitate the effects of occlusion  
202 by directly treating the aforementioned deficits found to be associated with amblyopia. Most  
203 therapy procedures are designed to remediate specific deficiencies in four main areas: fixation,  
204 spatial perception, accommodative efficiency, binocular function and oculomotor control.[5, 11-  
205 13]

206  
207 Lastly, some investigators have suggested that the use of vision therapy may reduce the  
208 likelihood of recurrence of the amblyopia.[4, 14] This may be particularly true with  
209 anisometropic amblyopia in which vision therapy can be used to improve binocular function.

### 210 **1.3 Synopsis of Study Design**

#### 211 212 Major Eligibility Criteria (See section 2.3 for a complete listing)

- 213 • Age 7 to <13 years
- 214 • Amblyopia associated with anisometropia, strabismus (comitant or incomitant), or both at  
215 the time of the eligibility examination
- 216 • No constant strabismus at near at the eligibility examination
- 217 • Visual acuity in the amblyopic eye between 49 and 71 letters inclusive (20/40 to 20/100  
218 inclusive) on the eETDRS
- 219 • Visual acuity in the sound eye of 79 or more letters on the eETDRS (20/25 or better)
- 220 • Inter-eye acuity difference of 15 or more letters (3 or more logMAR lines)
- 221 • At least 800 seconds of arc on the Randot Preschool Stereoacuity Test
- 222 • No previous vision therapy or orthoptics
  - 223 ➤ Previous or current amblyopia treatment with spectacles or contact lenses, patching or  
224 atropine is permitted
- 225 • Single vision spectacles, if needed, worn for at least 16 weeks or until visual acuity  
226 documented to be stable, (bifocals not allowed)
- 227 • The child has access to a computer on a daily basis (to use the home vision therapy  
228 software)

- 229 • No other family member is (or has been) enrolled in this study

230

### 231 Treatment Groups

232 The two treatment regimens for the 16-week treatment period are:

- 233 • 2 hours of daily patching combined with 1 hour daily of near activities (that includes 30
- 234 minutes of at-home active vision therapy) and weekly in-office active vision therapy
- 235 • 2 hours of daily patching combined with 1 hour of daily near activities (that includes 30
- 236 minutes of at-home control vision therapy) and weekly in-office control vision therapy

237

238 Patients in the study will be randomly assigned to active vision therapy or control vision therapy

239 in a 1:1 ratio. Patients and their parents will be masked to the treatment assignment for the

240 duration of the study.

241

242 Spectacle wear will be continued, if prescribed. Patients wearing contact lenses must be willing

243 to switch to spectacles for the duration of the study.

244

### 245 Sample Size

246 Sample size for this study will be 222 patients.

247

### 248 Visit Schedule

249 Weekly in-office treatment visits ( $\pm$  4 days) for 16 weeks and a masked examination at 17 weeks

250 ( $\pm$  1 week).

251

252 At each weekly visit, the patient will be queried regarding diplopia, visual acuity will be

253 measured in each eye, and in-office therapy will be completed. Visual acuity measurements may

254 be completed by a person who is unmasked to the patient's treatment assignment. At the 17-

255 week masked examination the patient will be queried regarding diplopia, and visual acuity,

256 stereopsis, and ocular alignment will be measured. The visual acuity and stereoacuity tests will

257 be performed by a person who is masked to the patient's treatment assignment. Patients also will

258 be asked whether they believe they were receiving active or control vision therapy.

259

### 260 Primary Analysis

261 The primary outcome measure is the proportion of patients with visual acuity of 20/25 or better

262 in the amblyopic eye at the 17-week masked exam. These patients will be considered treatment

263 responders. The primary analysis will consist of a comparison between the 2 treatment groups of

264 the proportion of treatment responders with adjustment for baseline visual acuity.

265

266 Secondary outcomes are stereoacuity at the 17-week masked exam, mean improvement in visual

267 acuity at the 17-week masked exam, and rate of improvement of visual acuity.

268

269 Sound eye visual acuity will be reported for each treatment group at the 17-week masked exam

270 as mean change from baseline, distribution of number of lines of change from baseline, and

271 number and proportion of patients losing 2 or more lines from baseline.

272

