411                   first of two consecutive measurements: 1) in current glasses, 2) in trial frames  
412                   with full correction of hypermetropia with cycloplegia, or 3) by having the  
413                   patient return in new glasses for the first measurement. The second acuity  
414                   measure does not have to be made through the same prescription as the first, if  
415                   the second measure is made through a more accurate prescription. *Note:*  
416                   *because this determination is a pre-study procedure, the method of measuring*  
417                   *visual acuity is not mandated, although eETDRS testing is preferred if done as*  
418                   *part of usual care.*

- 419                   ▪ Prior contact lens wear is permitted, but patients must be willing to switch to  
420                   spectacles for the duration of the study. Stability of visual acuity in spectacles  
421                   according to above criteria must be documented prior to enrollment.  
422                   ▪ Prior bifocal wear is permitted but patient must switch to and show stability  
423                   with single vision glasses before being enrolled in the study. There can be no  
424                   constant strabismus at near without the bifocals.
- 425   6. Near stereoacuity of 800 seconds of arc or better on the Randot Preschool Stereoacuity test
- 426   7. No previous home-based, office-based or computerized vision therapy or orthoptics
- 427   8. Previous or current amblyopia treatment with spectacles, contact lenses, patching, or  
428   atropine is permitted. At the time of enrollment the patient must be:
- 429       • currently patching for 2 hours per day, *or*
- 430       • ready to be switched to 2 hours per day of patching from another patching dose or  
431       from atropine, *or*
- 432       • not currently on treatment (other than spectacles or contact lenses) and ready to initiate  
433       patching for 2 hours per day.
- 434   The decision whether the patient is a suitable candidate to be switched to 2 hours per day of  
435   patching is at investigator discretion. Atropine treatment must be discontinued at least 2  
436   weeks prior to enrollment. Patients taking atropine may be switched to patching when  
437   atropine is discontinued and enrolled 2 weeks later, if the investigator does not wish to stop  

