## CHAPTER 8 SAMPLE SIZE AND STATISTICAL ANALYSIS

926  
927  
928  
929  
930  
  
931  
932  
933  
934  
935  
936  
937  
938  
939  
940  
941  
942  
943  
944  
945  
946  
947  
948  
949  
950  
951  
952  
953  
954  
955  
956  
957  
958  
959  
960  
961  
962  
963  
964  
965  
966  
967  
968  
969  
970  
971  
972  
973

The estimation of sample size and the statistical analysis plan are summarized below and detailed in separate documents. The analysis plan synopsis in this chapter contains the framework of the anticipated final analysis plan, which will supersede this section when it is finalized.

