### 8.1 Sample Size Estimation

The sample size estimate was computed based on a Fisher's exact test comparing proportions of patients in each treatment group with 20/25 or better visual acuity at the 17-week masked exam. Patients meeting this criterion will be considered a treatment success. Based on data from ATSS3 patients meeting eligibility criteria for the ATSS-VT study, it is estimated that 30% of patients in the control vision therapy group will have 20/25 or better visual acuity at the 17-week masked exam. To detect an absolute increase of 20% in the active vision therapy group to an outcome proportion of 50% with type I error of 5% (one-sided) and power of 90%, a total of 222 patients is needed. Patients who drop out of the study prior to completion of the 17 week masked exam will be counted as treatment failures in the primary outcome analysis; hence, no adjustment to the sample size has been made for dropouts.

A one-sided alpha is used as there is interest in testing only whether the outcome proportion for active vision therapy is significantly higher than for controls. If not higher, then there is no reason to use active vision therapy in clinical practice. An absolute increase in outcome proportion of 20% was chosen as the smallest improvement for which clinicians would be willing to use vision therapy in their clinical practice, given the time commitment and extra expense demanded of patients.

Counting dropouts as treatment failures may lower the expected proportion with treatment success in both treatment groups. In this case, the power for the primary outcome comparison is increased to greater than 90%. Adjustment for baseline visual acuity in the primary analysis also would be expected to improve statistical power.

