## 993 **8.2 Primary Outcome Analysis**

994

995 The primary analysis will consist of a comparison of proportions of patients in the two treatment  
996 groups who have 20/25 or better visual acuity at the 17-week outcome exam, with adjustment for  
997 baseline visual acuity, using logistic regression. The primary analysis will follow the ‘intent-to-  
998 treat’ principle in which patients are analyzed according to randomized treatment assignment,  
999 regardless of whether the treatment was actually received or completed. Dropouts will be  
1000 counted as treatment failures in the primary analysis.

1001

1002 A secondary analysis that counts study dropouts as treatment successes will be performed. The  
1003 true treatment effect must be bracketed within the estimated treatment difference obtained in the  
1004 primary analysis and this secondary analysis. If these are within 10% of each other using the  
1005 absolute difference, the primary analysis will be considered the definitive analysis. Otherwise,  
1006 both estimates will be included in the publication of study results along with a discussion of the  
1007 implications for study conclusions and patient management.

1008

1009 A secondary analysis that estimates the treatment difference based on study completers only also  
1010 will be performed.

1011

1012 The treatment effect in subgroups based on baseline factors will be assessed in preplanned  
1013 secondary analyses of the primary outcome. The subgroups of interest will be those based on  
1014 baseline amblyopic eye visual acuity, age, baseline stereoacuity, prior treatment, practice type  
1015 (ophthalmology or optometry), and treatment compliance (excellent/good or fair/poor). In  
1016 accordance with NIH guidelines, estimates of treatment effect by gender and race/ethnicity also  
1017 will be computed.

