  - 1080 • Enumeration and review of cases, if any, of ineligible patients enrolled;
  - 1081 • Estimation of the percentage of patients missing the treatment visit for each treatment  
1082 visit (overall, and by treatment);
  - 1083 • Distribution of number of treatment visits missed per patient (overall, by treatment group,  
1084 and by site)
  - 1085 • Estimation of mean and range for number of non-office visit days the home computer  
1086 therapy was used (by treatment group);
  - 1087 • Summary of patient progress through treatment protocol (number and percent of patients  
1088 in each phase by week of treatment and treatment assignment);
  - 1089 • Identification and review of patients making insufficient or very rapid progress with  
1090 treatment (patients appearing as outliers in the above table);
  - 1091 • Enumeration and review of all cases, if any, with adverse events (diplopia, reverse  
1092 amblyopia, development of a new ocular deviation);
  - 1093 • Estimation of retention and dropout rates of enrolled patients at 17 weeks (overall and by  
1094 center);
  - 1095 • Estimation of percentage of patients with valid outcome data for each outcome at 17  
1096 weeks (overall and by center);
  - 1097 • Estimation of the percentage of patients in each treatment group who correctly and  
1098 incorrectly identify their treatment group assignment;
  - 1099 • Estimation of the percentage of patients in the control group not classified as treatment  
1100 responders who elect to undergo a course of active therapy.

1101  
1102 Patients will be classified into 3 groups according to prior treatment status for the purpose of  
1103 estimating recruitment rate within each of the groups. These 3 groups are:

- 1104 • Patients who were not treated for amblyopia within 6 months prior to enrollment;
  - 1105 • Patients who were treated within the past 6 months who initially had severe amblyopia  
1106 and were enrolled in the study after improvement to moderate amblyopia; and
  - 1107 • All other patients who were treated within the past 6 months.
- 1108

1109 The purpose of this stratification is to determine which, if any, of these groups has sufficient  
1110 numbers of patients that they could be targeted for a full-scale trial of vision therapy.

1111

1112 Outcome data consist of data from the testing procedures at the 17-week examination as  

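### The primary logistic model adjusts for baseline acuity alone; adding age and prior amblyopia treatment would be a small, low-cost gain in efficiency, not the correction of an error

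*Protocol*

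**What the plan says.** Section 1.3 (Primary Analysis) compares the arms on "the proportion of treatment responders with adjustment for baseline visual acuity". Section 8.2 repeats this as a comparison adjusted for "baseline visual acuity, using logistic regression". No other covariate is named.

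Other parts of the protocol bear on age and prior treatment:

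- **Eligibility (2.3, criterion 8).** Entry is open after "Previous or current amblyopia treatment with spectacles, contact lenses, patching, or" atropine. At enrolment a child may already be patching 2 hours a day, be switching from another patching dose or from atropine, or be off treatment and ready to start patching.
- **Data collected (2.4.1).** Date of birth and prior amblyopia therapy are recorded at enrolment.
- **Randomisation (2.5).** Permuted blocks are stratified by site only.
- **Subgroups (8.2).** The treatment effect will be examined by "baseline amblyopic eye visual acuity, age, baseline stereoacuity, prior treatment, practice type" and treatment compliance.
- **Feasibility (8.8).** "Patients will be classified into 3 groups according to prior treatment status for the purpose of" estimating recruitment within each group.
- **Status of Chapter 8.** It is described as the framework of the "anticipated final analysis plan, which will supersede this section when it is finalized".
- **Power (8.1).** The sample size rests on "type I error of 5% (one-sided) and power of 90%, a total of 222 patients". The section adds that adjusting for baseline acuity should raise power further.

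**The concern.** Section 8.1 already accepts that adjusting for a baseline predictor buys power. The same argument covers any other pre-randomisation predictor of reaching 20/25, and two plausible ones are already on the enrolment form.

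- **Prior treatment.** For a child already patching 2 hours a day, the patching part of both regimens is a continuation. For an untreated child it is new. A child who is still at 20/40 to 20/100 after earlier treatment may be harder to bring to 20/25.
- **Age.** Section 1.2 reports response to an earlier patching-based regimen in 53% of 7 to 12 year olds. In 13 to 17 year olds it was 25%.

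Neither factor is balanced by the randomisation beyond what chance provides. If they do predict outcome, leaving them out of a logistic model costs some power. It also leaves their chance imbalance in the primary estimate. Should the arms differ visibly on prior treatment, adjustment decided after the fact would be open to dispute.

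**Working it through.** **1. The plan's own figure.** Inputs from 8.1: control 30% ("it is estimated that 30% of patients in the control vision therapy group"), active 50%, one-sided 5%, power 90%.

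- Without continuity correction: n per arm = [1.645 × √(2 × 0.4 × 0.6) + 1.282 × √(0.3 × 0.7 + 0.5 × 0.5)]² / 0.2² = 100.9, so 101 per arm, 202 in total.
- With continuity correction: (100.9 / 4) × [1 + √(1 + 4 / (100.9 × 0.2))]² = 110.7, so 111 per arm, **222 in total**.
- Full enumeration of the one-sided Fisher exact test at 111 per arm gives power 0.9001.

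The figure reproduces. It comes from an unadjusted test, so the covariate set cannot affect it.

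**2. Power with and without the extra covariates.** The protocol gives no odds ratios (OR) for age or prior treatment, so these are assumed over a range. All simulations use 222 children and a one-sided 5% test. A and B use Wald tests and hold marginal success at 30% and 50%.

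*Simulation A* (5,000 trials per setting; acuity OR 1.08 per letter; ages uniform from 7 to 13; half previously treated):

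| Age OR per year | Prior treatment OR | Acuity only | Acuity + age + prior treatment | Information ratio |
|---|---|---|---|---|
| 0.90 | 0.6 | 93.1% | 93.5% | 1.02 |
| 0.85 | 0.4 | 92.8% | 93.9% | 1.05 |
| 0.80 | 0.3 | 93.1% | 94.5% | 1.09 |

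The information ratio is the squared ratio of mean z statistics, so 1.09 is worth about 9% more patients. With no effect of either factor, the cost was about 0.1 point.

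*Simulation B* (4,000 trials per setting; acuity OR 2.23 per SD; half previously treated):

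| Age OR per SD | Prior treatment OR | Unadjusted | Acuity only | All three |
|---|---|---|---|---|
| 1.00 | 1.00 | 91.6% | 94.7% | 94.6% |
| 0.85 | 0.70 | 92.0% | 94.5% | 94.6% |
| 0.75 | 0.50 | 92.5% | 95.1% | 95.6% |
| 0.60 | 0.35 | 92.2% | 94.0% | 95.8% |

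On these assumptions acuity alone adds 1.8 to 3.1 points over no adjustment. The other two factors add −0.1 to +1.8.

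*Simulation C* used the coding suggested below: continuous age and a three-level prior-treatment factor. From no effect to strong assumed effects, power changed by about −0.3, +0.2, +1.0 and +1.6 points. Information ratios ran from 1.00 to 1.09, and type I error stayed near 5%.

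Each power figure in A has a simulation standard error of about √(0.93 × 0.07 / 5,000) = 0.4 point, so changes of a few tenths should be read as roughly zero.

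**3. Chance imbalance in prior treatment** (assumed 50% prevalence, 111 per arm).

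- SD of the between-arm difference: √(0.25 × 2 / 111) = 6.7 points; 95% range ±1.96 × 6.7 = ±13 points.
- Control success in Simulation A, treated v not: 25% v 35%, 21% v 39%, 19% v 41%, so gaps of 10, 18 and 22 points. Typical shift: 0.067 × 10 = 0.7 to 0.067 × 22 = 1.5 points.
- At the 95% extreme, with gaps of about 8, 16 and 24 points (ORs 0.70, 0.50 and 0.35): 0.13 × gap = about 1, 2 and 3 points, against a 20-point target.
- Sampling standard error of the raw difference: √(0.3 × 0.7 / 111 + 0.5 × 0.5 / 111) = 6.4 points. The imbalance therefore accounts for (0.7 / 6.4)² = 1% to (1.5 / 6.4)² = 5% of that variance.

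**The case against.** Adjusting for the baseline value of the outcome measure is a standard and valid analysis. No figure in the protocol is wrong and no error rate is affected. Four further points deserve weight.

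- **Prognosis is not shown.** A reader might infer that the protocol itself treats age and prior treatment as predictors of outcome. It does not. The 8.2 list concerns differences in treatment effect, and the 8.8 groups serve recruitment estimates. The age contrast in 1.2 uses a different endpoint and reaches outside 7 to <13 years, and with optical correction alone the two age bands barely differ (25% v 23%). The nearest hint is in 8.1, which assumes 10% success for control non-responders given active therapy. Against 30% for controls that is an OR of (0.1/0.9) / (0.3/0.7) = 0.26, but it is a planning assumption for a group selected for non-response.
- **Not immovable.** Chapter 8 yields to a final analysis plan, which is not at hand. That clause covers Chapter 8 only, so the synopsis in 1.3 would still name acuity alone.
- **Chance imbalance is not bias.** It is already inside the standard error, as step 3 shows.
- **The choice of covariates is a judgement.** Baseline stereoacuity and practice type stand in the same list. The 8.8 groups also use a six-month history, whereas criterion 8 turns on current treatment, so the two classifications do not coincide.

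All four stand. They reduce the point to an optional one but do not remove it: the data exist, the gain is non-negative apart from a few tenths of a point, and the protocol's own reason for adjusting applies.

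**Conclusion.** The primary model leaves out two baseline factors that are recorded, not stratified and plausibly prognostic. Adding them changes power by about 0 to 2 points, equivalent to about 0 to 9% more patients, from a base already above 90%. The upper end needs strong assumed effects, such as a prior-treatment OR of 0.3 to 0.35. All of this rests on assumed odds ratios and, in A and B, on half the children being previously treated.

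A reader might go further and infer that the stated analysis is biased, underpowered or invalid. The documents support none of these: the acuity-adjusted test is sound, 222 reproduces, and every simulated model exceeds the planned power. This is an optional, low-cost efficiency improvement.

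**What to change.** In Sections 1.3 and 8.2, and in the 8.7.1 ANCOVA, prespecify adjustment for baseline visual acuity, age as a continuous variable, and prior amblyopia treatment in categories fixed before unmasking. The three groups in 8.8 are one workable choice; categories built on the current-treatment states in criterion 8 are another.

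Report the adjusted difference in proportions from the logistic model. The conditional odds ratio changes meaning as covariates are added, while 8.1 and 8.2 reason in absolute differences.

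The cost is a sentence of wording in each place, with no new data. The model gains two parameters with a binary prior-treatment factor or three with a three-level one, against about 33 + 56 = 89 expected responders. If neither factor predicts outcome, the loss is a few tenths of a power point at most.
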